5.3 LIFESTYLE CONSIDERATIONS

While participating in this trial, participants are asked to:

- Refrain from alcohol consumption of more than 20 g/2 units/2 standard drinks per day from 24 hours before inoculation until the EOS.
- Abstain from any illicit drug habituation until the EOS.
- Abstain from any alcohol and tobacco use for the duration of clinical trial unit confinement.
- Refrain from tobacco use of more than five cigarettes or equivalent per day until the EOS.
- Refrain from excessive consumption of beverages or food containing xanthine bases including Red Bull, chocolate, coffee etc. (more than 400 mg caffeine per day, equivalent to more than 4 cups of coffee per day).
- Refrain from consumption of Seville oranges, and grapefruit or grapefruit juice from 7 days prior to inoculation until EOS.
- Refrain from consumption of quinine containing foods/beverages such as tonic water and lemon bitter from inoculation until the EOS.
- Abstain from strenuous exercise for 24 h before each blood collection for clinical laboratory tests. Participants may participate in light recreational activities during studies.

5.4 SCREEN FAILURES

Healthy candidate participants who do not fulfil all the inclusion criteria, and/or fulfil any of the exclusion criteria should not be enrolled, however unscheduled visits may be planned to assess, confirm, and follow-up on out-of-range clinical laboratory test, vital sign, or ECG values that determine a participant's eligibility. A positive urine drug screen should only be re-tested if there is a strong rationale for doing so (for example, false positive). The result of the re-test must be considered for participant eligibility and must be available prior to inoculation or pyronaridine administration. In case of doubt, the PI is to confer with the Medical Monitor for agreement.

If a participant does not meet all eligibility criteria (is a screen failure) but at some point in the future is expected to meet the eligibility criteria, the participant may be rescreened on one occasion only. Participants who are rescreened should be assigned the same screening number as for the initial screening.

A minimal set of screen failure information is required to ensure transparent reporting of screen failure participants, to meet the Consolidated Standards of Reporting Trials (CONSORT) publishing requirements and to respond to queries from regulatory authorities. Minimal information includes demography, screen failure details, eligibility criteria, and any serious adverse event (SAE). Screen failure information will not be entered into the eCRF. Participants who fail screening due to an underlying medical condition previously unknown to them will be reimbursed for their time, and provided with the appropriate referrals for guidance and counselling for their condition.

5.5 STRATEGIES FOR RECRUITMENT AND RETENTION

It is anticipated that up to 18 healthy, adult, malaria-naïve participants will need to be dosed with pyronaridine in this trial. It is anticipated that a total of 6 reserve participants will be required to ensure adequate participant numbers.

Participants will be recruited by general or trial specific advertising via print, radio, social media, or poster media, as approved by the HREC(s). No restrictions will apply for ethnic or racial categories.

Participants who withdraw or are withdrawn from the trial will be compensated on a fractional basis for their involvement unless they are withdrawn as a consequence of their misconduct.

Reserve participants who do not participate in the trial will be compensated for the inconvenience associated with their attendance for screening and attendance on Day 0.

The monetary value of the compensation for each trial part is documented in the respective Participant Information Sheet.

6 STUDY INTERVENTIONS

6.1 STUDY INTERVENTIONS ADMINISTRATION

The following sections describe the study interventions. A pharmacy manual with detailed information will be finalised and approved prior to study start.

6.1.1 STUDY INTERVENTIONS DESCRIPTION

IMP

Pyronaridine is a benzonaphthyridine derivative first synthesized in China in 1970. Pyronaridine has been used in China for the treatment of malaria as a single agent for more 50 years. The antimalarial activity of pyronaridine is thought to occur primarily due to inhibition of hemozoin formation, which results in accumulation of toxic hematin in the parasite food vacuole.

It was developed as an oral fixed-dose combination therapy with artesunate (an artemisinin derivative) for the treatment of acute uncomplicated *P. falciparum* malaria and blood stage *P. vivax* (Pyramax®, co-developed by Medicines for Malaria Venture, Geneva, Switzerland and Shin Poong Pharmaceutical Co., Ltd, Seoul, South Korea). Pyramax® received a positive opinion by European Medicines Agency (EMA) under the article 58 process [evaluation of medicinal products intended exclusively for markets outside the European Community] in 2012 and 2015. Pyramax® was also added to the World Health Organization's (WHO) Model List of Essential Medicines (EML) and Model List of Essential Medicines for Children (EMLc) in 2017. Its procurement and use at a country level is further supported by a WHO Information Note of October 2019. Pyramax® is currently approved for use in 29 countries, although it has not yet been registered for use in Australia. For the current study, pyronaridine tablets for oral

administration will be manufactured by Shin Poong Pharmaceutical Co., Ltd, licence holder and manufacturer of Pyramax.

Challenge agent

A *P. falciparum* 3D7 master cell bank (MCB) was produced from a participant with type O Rh(D) negative blood who was infected with the parasite by mosquito bite. Blood was collected and aliquoted into cryovials and stored in liquid nitrogen under controlled conditions. Refer to the *P. falciparum* 3D7 IB for more details. A cryovial will be retrieved from storage, thawed, and used to aseptically prepare the intravenous inoculum at Q-Gen Cell Therapeutics (QIMR Berghofer).

Rescue Antimalarial medications

Riamet® (Novartis Pharmaceuticals Australia Pty Ltd) is an oral fixed dose combination therapy containing artemether and lumefantrine. Riamet® is registered in Australia for the treatment of acute uncomplicated malaria.

Primacin® (Boucher & Muir Pty Ltd) contains the active ingredient primaquine phosphate. Primaquine phosphate is an 8-aminoquinoline effective against the sexual forms (gametocytes) of *Plasmodium* species which are responsible for transmission to mosquitoes. Primacin® is registered for use in Australia.

Malarone® (GlaxoSmithKline Australia Pty Ltd) is an oral fixed dose combination therapy containing atovaquone and proguanil hydrochloride. Malarone® is registered in Australia for the treatment of acute uncomplicated malaria.

Artesunate (powder and diluent for reconstitution, imported by Link Pharmaceuticals) is an artemisinin derivative; the intravenous formulation is typically used to treat severe malaria. Although parenteral artesunate does not currently have marketing approval in Australia, the Therapeutic Goods Administration (TGA) allows importation of artesunate for Category A use in patients with severe malaria under the Special Access Scheme (SAS).

6.1.2 DOSING AND ADMINISTRATION

IMP

Pyronaridine tablets will be administered after an overnight fast of ≥ 8 hours as a single oral dose with 240 mL of water on Day 8. Pyronaridine will not be administered if any of the criteria described in 7.1.1 has been met. In this situation participants will be administered antimalarial rescue treatment. Different doses of pyronaridine will be tested across and within cohorts, with the doses to be determined by the SDRT based on the emerging data during the study. The maximum dose to be tested in the study will be no more than 720 mg (4 tablets). The minimum dose to be tested in the study will be no less than 180 mg (1 tablet).

Challenge Agent

The malaria challenge agent, containing an estimated $\sim 2,800$ viable *P. falciparum* 3D7 parasite-infected erythrocytes in a volume of 2 mL, will be administrated intravenously on Day 0. The actual number of

parasites inoculated will take into account the loss of viability resulting from cryopreservation, storage and thawing. Participants will undergo intravenous cannulation with a 20 or 22 gauge cannula. Placement and patency will be checked by flushing the vein with 5-10 mL of clinical grade saline. The inoculum will be injected, and the cannula again flushed with 5-10 mL of clinical grade saline. The cannula will then be removed, and haemostasis ensured by use of an appropriate dressing. An extra syringe will be prepared to quantify the parasite count of the challenge agent by malaria 18S qPCR.

Rescue Antimalarial medications

Compulsory definitive antimalarial treatment with Riamet® for all participants will be initiated on Day 47±2. Treatment may be initiated earlier in accordance with the criteria described in Section 4.1. Riamet® tablets will be administered as six oral doses of four tablets (total course of 24 tablets) given over a period of 60 hours (total dose of 480 mg artemether and 2.88 g lumefantrine). Participants will be reminded of the potential side effects of Riamet® and will be given the CMI for Riamet®.

Participants may be treated with Primacin® if gametocytaemia is suspected from parasite lifecycle stage qRT-PCR at the Investigator's discretion, to ensure clearance of gametocytes. If needed, participants will be administered a single oral dose of six Primacin® tablets (total dose 45 mg primaquine) with food, unless G6PD deficient in which case a low dose of 15 mg (two tablets) will be administered.

Participants will be reminded of the potential side effects of Primacin® and will be given the CMI for Primacin®.

If an allergy or contraindication to Riamet® develops, Malarone® may be administered at the Investigator's discretion. A treatment course consists of four tablets administered once daily for three days (total dose of 3 g atovaquone and 1.2 g proguanil hydrochloride). Participants will be reminded of the potential side effects of Malarone® and will be given the CMI for Malarone®.

Intravenous artesunate may be administered if the participant vomits or cannot tolerate oral drugs. In this rare event, the participant will be admitted to hospital for treatment. Artesunate will be administered as 2.4 mg/kg IV bolus on admission, with repeat dosing at 12 hours and 24 hours, then once daily until oral therapy is possible.

6.2 PREPARATION/HANDLING/STORAGE/ACCOUNTABILITY

6.2.1 ACQUISITION AND ACCOUNTABILITY

The clinical trial unit pharmacist or delegate, as nominated by the PI, is responsible for maintaining accurate study intervention accountability records throughout the study. Study interventions include the malaria challenge agent, the IMP (pyronaridine), and the antimalarial rescue treatments. Dispensing, accountability and documentation will be in accordance with the clinical unit standard procedures.

All products will be inventoried upon receipt by the clinical trial unit pharmacist. The condition of the products at the time of receipt by the pharmacist will be documented, as will the time restrictions of use for the syringes containing the challenge agent. The lot numbers and expiry dates of all study interventions will be documented. The clinical trial unit pharmacist or delegate will ensure that the received products are the specified formulation.

The storage, handling and the disposal of the challenge agents will be in accordance with approved procedures. All dosages prescribed and dispensed to the participants and all dose changes during the study must be recorded in the eCRFs and accountability logs. All drug supplies are to be used only in accordance with this protocol, and not for any other purpose. All used medications will be fully documented. Used and unused drug containers must be destroyed at the unit once drug accountability is final and has been checked by the Sponsor or its delegate, and written permission for destruction has been obtained from the Sponsor.

Study products and study accountability logs will be available to the Sponsor or their representative as part of the study monitoring procedures. Upon completion of the study, copies of all study drug management records will be provided to the Sponsor. Original records will be maintained at the clinical unit with the rest of the study records.

IMP

Pyronaridine tablets will be manufactured by Shin Poong Pharmaceutical Co., Ltd, Seoul, South Korea and acquired by the clinical unit.

Challenge agent

Aliquots of the *P. falciparum* 3D7 MCB are stored in liquid nitrogen under controlled conditions. On the day of inoculation, cryovials will be retrieved from storage and used to aseptically prepare the challenge agent at Q-Gen Cell Therapeutics (QIMR Berghofer). The clinical trial unit pharmacist or designee will be responsible for maintaining the accurate *Plasmodium falciparum* 3D7 Challenge Agent Accountability Log as per clinical trial unit standard operating procedures (SOPs).

Rescue Antimalarial medications

Riamet® (distributed by Novartis Pharmaceuticals Pty Ltd), Primacin® (distributed by Boucher & Muir Pty Limited), and Malarone® (distributed by GlaxoSmithKline Australia Pty Ltd) will be acquired by the clinical

trial unit. Artesunate for intravenous administration is available within the Central Pharmacy of Queensland Health.

6.2.2 FORMULATION, APPEARANCE, PACKAGING, AND LABELING

The contents of the dispensing labels for the IMP, the malaria challenge agent, and the antimalarial rescue treatments will be in accordance with all applicable regulatory requirements.

IMP

Pyronaridine tablets, each containing 180 mg pyronaridine tetraphosphate, are orange, round, film-coated scored tablets. Excipients include: microcrystalline cellulose, crospovidone, mannitol, magnesium stearate, talc, Hypromellose 2910, macrogol 6000 and Opadry OY-S-23068. Tablets are packaged in aluminium/PVC/aluminium-oPA foil blisters containing 9 tablets per blister. The blisters are packed into cartons.

Challenge agent

The malaria challenge agent will contain parasitised and unparasitised erythrocytes, resuspended in 0.9% Sodium Chloride Intravenous Infusion, in a total volume of 2 mL in syringes. The syringes will be double contained following preparation and labelled in accordance with GCP guidelines. Labelling is in accordance with PIC/S Annex 13.

Rescue Antimalarial medications

Riamet® tablets (each containing 20 mg artemether/120 mg lumefantrine) are yellow, round, flat tablets marked with N/C and a score line on one side and CG on the other side. Each carton contains 24 tablets.

Primacin® tablets (each containing 13.2 mg primaquine phosphate equivalent to 7.5 mg primaquine) are round, flat, orange uncoated tablets available in bottles of 28 or 56 tablets.

Malarone® tablets are round, pink and film-coated, and are engraved with “GX CM3”. Malarone® tablets are supplied in blister packs of 12 or 24 tablets.

Artesunate powder for reconstitution is supplied in vials containing 60 mg artesunate. Each vial is reconstituted with an ampoule (1 mL) of sodium bicarbonate 5%. Sodium chloride 0.9 % (5 mL) is then added to reconstituted artesunate vial to create a 10 mg/mL solution (total volume 10 mL).

6.2.3 PRODUCT STORAGE AND STABILITY

All drugs will be held in appropriate locked storage conditions at the clinical trial unit until required.

IMP

Pyronaridine tablets are to be stored below 25°C in the original package. The shelf life is 18 months.

Challenge agent

The *P. falciparum* 3D7 challenge agent is prepared at Q-Gen on inoculation day (Day 0). The time between preparation of the challenge agent and administration to the participant will be a maximum of 4 hours. The syringes containing the challenge agent will be stored in a temperature monitored validated transport container at 2-15°C during transportation from Q-Gen to the clinical trial unit and will be immediately transferred to a temperature monitored onsite refrigerator (2-15°C). The clinical trial unit pharmacist will document receipt conditions and time restrictions of use. The challenge agent will then be dispensed to participants as per written prescription. Transporter logs should be provided to the Sponsor.

Rescue Antimalarial medications

Riamet® tablets are to be stored below 30°C and protected from moisture. Primacin® tablets are to be stored below 25°C. Malarone® tablets are to be stored below 30°C. The reconstituted artesunate for intravenous administration should be prepared freshly for each administration and should not be stored.

6.2.4 PREPARATION

IMP

No preparation is required for the pyronaridine tablets for oral administration.

Challenge agent

The challenge agent will be prepared aseptically at Q-Gen from frozen cryovials of the *P. falciparum* 3D7 MCB by nominated QIMR Berghofer staff members. The erythrocytes will be thawed, washed, resuspended in saline, diluted in a final volume of 2 mL of clinical grade saline, and dispensed into syringes. Any remaining unused erythrocytes will be discarded as per approved SOPs.

Rescue Antimalarial medications

Riamet®, Primacin® and Malarone® are available as tablets and no preparation is required. Artesunate for intravenous administration will be prepared according to manufacturer's instructions within the hospital setting immediately prior to administration.

6.3 MEASURES TO MINIMIZE BIAS: RANDOMISATION

All participants will receive an identification number (screening number) as soon as they have signed the informed consent form. Participants who meet the eligibility criteria and are enrolled in the study will be assigned an enrolment number on Day 0 immediately prior to administration of the malaria challenge agent. Participants will be randomised within each cohort to a dose group on Day 8, immediately prior to administration of the IMP. This is an open label study and therefore no blinding will be performed.

6.4 STUDY INTERVENTIONS COMPLIANCE

The investigator will administer the malaria challenge agent intravenously at the clinical trial unit on Day 0.

The IMP (single oral dose of pyronaridine) will be administered at the clinical trial unit on Day 8 under direct observation by staff.

The first dose of Riamet® will be administered at the clinical trial unit under direct observation by staff. The subsequent five doses may be taken at home. Participants will receive a phone call or text message from the clinical trial unit staff to ensure compliance.

If Primacin® is required at any time point after the confinement period, it will be administered at the clinical trial unit under direct observation by staff.

If Malarone® is required, the first dose will be administered at the clinical trial unit under direct observation by staff. The subsequent two doses may be taken at home.

Participants will receive a phone call or text message from the clinical trial unit staff to ensure compliance. If a participant requires intravenous artesunate, the participant will be admitted to hospital for treatment.

6.5 CONCOMITANT THERAPY

Concomitant medications, treatments and procedures are those occurring from the time of administration of the malaria challenge agent (Day 0), until the final study visit. Those occurring prior to Day 0 are classified as prior medications, treatments and procedures. Medications taken within 28 days before Day 0 will be recorded as prior medication.

On Day 0, participants will be questioned in relation to relevant aspects of compliance with the study protocol, including drug intake since their screening visit. Details of all drugs taken (prescription and over-the-counter, systemic and topical administration) will be recorded at this time and appropriate action taken.

From Day 0 until the EOS visit, no medications will be permitted to be taken without the approval of the PI (with the exception of contraceptives and ibuprofen). Ibuprofen (preferred) may be administered at doses of up to 1.2 g/24 hours, or paracetamol up to 4 g/24 hours with Investigator approval, for treatment of headache or other pain if required. Ibuprofen is the preferred treatment for headache or pain. To minimise the risk of liver enzyme elevation, paracetamol is to be avoided if possible; however paracetamol may be required by some participants and as such is not a prohibited substance. All other medications will be assessed by the PI on a case by case basis with regard to the participant's wellbeing and potential for the medication to interfere with study interventions.

Any medication taken during the study for treatment of a medical condition or AE is to be recorded in the concomitant medication pages in the eCRF. The exact dose, route and timing of each dose should be recorded.

6.5.1 RESCUE MEDICINE

Antimalarial rescue treatments used in this study are Riamet®, Primacin® (if required), Malarone® (if required), and IV artesunate (if required). Details are provided in Sections 6.1 and 6.2.

7 STUDY INTERVENTIONS DISCONTINUATION AND PARTICIPANT DISCONTINUATION/WITHDRAWAL

7.1 DISCONTINUATION OF STUDY INTERVENTIONS

The Sponsor, SDRT, PI, approving HREC(s), and the TGA independently reserve the right to discontinue the trial at any time for safety or other reasons. This will be done in consultation with the Sponsor where practical. In the event of premature trial termination or suspension, the above-mentioned parties will be notified in writing by the terminator/suspender stating the reasons for early termination or suspension (with the exception of the TGA as it is the Sponsor's responsibility to notify regulatory authorities). After a decision to prematurely terminate the trial or to suspend the trial, the Sponsor and the PI will ensure that adequate consideration is given to protecting the participants' interest and safety. The PI must review all participants as soon as practicable and complete all required records.

7.1.1 CRITERIA FOR ADMINISTRATION OF RESCUE MEDICATION INSTEAD OF IMP DOSING ON DAY 8

Once inoculated, it is expected that some study participants will experience malaria symptoms and biological changes (i.e. mild ALT/AST elevation, mild decrease in neutrophil count). Therefore, the following criteria should be considered as guidance for the decision not to proceed with pyronaridine dosing on Day 8 and preference for rescue medication instead:

1. A participant experiences an SAE or \geq CTCAE Grade 3 event (e.g. inoculum-related events such as lymphopenia or neutropenia).
2. A participant has an ALT or AST $> 2 \times$ ULN or total bilirubin $> 1 \times$ ULN.
3. A participant with positive alcohol or urine drug screen.
4. A participant who tests positive for SARS-CoV-2 (section 8.3.7).
5. A participant with one of the following ECG abnormalities:
 - QTcF at any time >480 msec,
 - Bundle branch block (except right bundle branch block that was present prior to pyronaridine administration),
 - Any arrhythmia, except:
 - a. *Sinus bradycardia that is clinically asymptomatic, and not associated with any other relevant ECG abnormalities,*
 - b. *sinus tachycardia that is clinically asymptomatic, and not associated with any other relevant ECG abnormalities,*
 - c. *Respiratory sinus arrhythmia,*
 - d. *Wandering atrial pacemaker,*

- e. *Isolated, single premature atrial/ventricular complex (i.e., no bigeminy, trigeminy, couplets, triplets or salvos) that does not occur more than once in a particular ECG tracing.*
6. The Investigator and delegates may also decide not to proceed with pyronaridine dosing based on other safety signals (clinical, ECG, vitals and laboratory tests) not included in the above criteria if there is a risk perceived for the study participants.

In the event that participants are dosed with antimalarial rescue treatment instead of pyronaridine, participants will be administered their first dose of antimalarial rescue treatment at the clinic, but will then be able to return home. The participant will be contacted daily via phone to check that each dose of antimalarial treatment is being taken, and to ascertain any adverse events. Following antimalarial rescue treatment, blood will be taken for 18S qPCR until at least one negative result is obtained. No further bloods will be collected for drug concentration. Blood sampling for haematology and biochemistry and for future malaria research (if the participant has consented) will occur as scheduled until day 29 ± 1 . The EOS visit may be brought forward to day 29 ± 1 , at the discretion of the PI.

If more than two discontinuations pre-IMP administration occur, additional participants may be recruited to subsequent cohorts to replace the discontinued participants on agreement with the study Sponsor.

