7.2 VOLUNTEER DISCONTINUATION/WITHDRAWAL FROM THE STUDY

Participants are free to withdraw from participation in the trial at any time upon request.

An Investigator may discontinue or withdraw a participant from the trial for the following reasons:

- Pregnancy
- Significant trial intervention non-compliance
- If any clinical AE, laboratory abnormality, or other medical condition or situation occurs (or an exclusion criteria is revealed that was not previously recognised) such that continued participation in the trial would not be in the best interest of the participant

The reason for participant discontinuation or withdrawal from the trial will be recorded on the eCRF. Participants who sign the informed consent form and are randomised but do not receive malaria inoculation may be replaced. Participants who sign the informed consent form, and are randomised and receive malaria inoculation, and subsequently withdraw, or are withdrawn or discontinued from the trial, may be replaced after mutual agreement between the Sponsor and the PI. The decision regarding the replacement of participants will be documented.

Participants who have been inoculated and indicate they wish to withdraw from the trial must complete the full course of definitive antimalarial treatment.

Participants will be reminded of the importance of completing their antimalarial treatment. Additionally, the PI will demonstrate due diligence in following up with the participant to ensure antimalarial therapy has been completed successfully. Participants may also be treated with Primacin™ if gametocytaemia is suspected from parasite lifecycle qRT-PCR or by the presence of stable low-level parasitaemia to ensure complete clearance of gametocytes. The decision to administer Primacin™ will be made by the PI in consultation with the medical monitor.

If a participant is withdrawn from the trial, the Sponsor will be informed immediately. If there is a medical reason for withdrawal, the participant will remain under the supervision of the PI until satisfactory health has returned, or medical/clinical care has been transferred to the participant's general practitioner or to a hospital consultant.

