The screening will be conducted within 28 days prior to the inoculation day and will include all activities listed below:

- A screening number will be assigned to each participant (as per clinical trial unit standard format).
- Elicit a complete medical history and use of medications.
- Elicit a social history including recreational drug, alcohol and tobacco use.
- Elicit demographic data.
- Record body height and weight.
- Perform alcohol breath test.
- Perform urine drug screen.
- Perform complete physical examination.
- Ask participant to complete the Beck Depression Inventory.
- Assess the cardiovascular disease risk (as per the Australian Absolute Cardiovascular Disease Risk Calculator).
- Record vital signs (supine and standing blood pressure and heart rate).
- Obtain a 12-lead ECG.
- Collect urine for urinalysis.
- Collect NPA for SARS-CoV-2 testing (if screening visit is conducted two days prior to inoculation).
- Collect blood samples for haematology and biochemistry (including lipids for cardiovascular risk factor), red cell antibodies, quantitative G6PD, serology and coagulation profile.
- Perform serum β -hCG pregnancy test for all females, and FSH test for post-menopausal females.

- Verify participant meets inclusion/exclusion criteria.

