8.1.5 INPATIENT OBSERVATION AND IMP ADMINISTRATION (DAY 8 TO DAY 12)

Participants will be admitted to the clinical trial unit for single-dose administration of pyronaridine on Day 8 when parasitaemia for the majority of participants is expected to be above 5,000 parasites/mL.

The following procedures will occur at admission to the clinical trial unit (before pyronaridine administration):

- Perform RAT for SARS-CoV-2 testing
- Perform abbreviated physical examination.
- Obtain and review a 12-lead ECG.
- Record vital signs.
- Perform and review urine β -hCG pregnancy test for WOCBP.
- Record AEs and use of concomitant medications.
- Perform and review alcohol breath test and urine drug screen.
- Review haematology and biochemistry results from Day 7 am collection.
- Cannulate participants with an indwelling intravenous (18 or 20 gauge) cannula.
- Collect blood samples for
 - haematology and biochemistry,
 - malaria 18S qPCR,
 - parasite viability *ex vivo* growth,
 - drug concentration (baseline sample),
 - malaria future research sample (if participant consented)

The following procedures will occur after pyronaridine administration:

- Administer the relevant pyronaridine dose under direct observation.
- Follow up participants as in-patients for up to 96 hours to ensure tolerance of pyronaridine and adequate clinical response.
- Perform symptom-directed physical examination if clinically indicated.
- Record vital signs three times a day (approximately 6 – 8 hours apart) whilst confined.
- Obtain 12-lead ECG once daily while confined.
- Collect blood for haematology and biochemistry at 72 hours post-pyronaridine administration.
- Collect blood for malaria 18S qPCR following pyronaridine administration at 4, 8, 12, 16, 20, 24, 30, 36, 42, 48, 60, 72, 84 and 96 hours (see section 8.4 for time allowed time windows).
- Collect blood samples for drug concentration at 1, 2, 3, 4, 6, 8, 12, 16, 20, 24, 30, 36, 42, 48, 60, 72, 84 and 96 hours (see section 8.4 for time allowed time windows).
- Collect blood for parasite viability *ex vivo* growth at 4, 8, 12, 16, 20, 24, 48, 72 and 96 hours (see section 8.4 for time allowed time windows).
- Record AEs and use of concomitant medications.

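### In Protocol 7.1.1 item 5 the right bundle branch block exemption is vacuous before the only dose, so right bundle branch block new since inoculation is not a listed Day 8 stop

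*Protocol*

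**What the plan says.** **Protocol 7.1.1** governs the choice between pyronaridine and rescue medication on Day 8. It opens with "Once inoculated, it is expected that some study participants will experience malaria symptoms and biological changes" and describes its list as guidance. **Protocol 6.1.2** is firmer about the same list: "Pyronaridine will not be administered if any of the criteria described in 7.1.1 has been met".

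Item 5 of the list holds the ECG criteria: QTcF above 480 msec, arrhythmia with named exceptions, and "Bundle branch block (except right bundle branch block that was present prior to pyronaridine administration". Item 6 adds that the Investigator and delegates "may also decide not to proceed with pyronaridine dosing based on other safety signals (clinical, ECG, vitals and laboratory tests" that the list does not name.

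**ECG timing.** At screening (8.1.1) the instruction is "Obtain a 12-lead ECG", and 8.1.3 repeats it for Day 0 before inoculation. At Day 8 admission, before dosing, 8.1.5 requires staff to "Obtain and review a 12-lead ECG". The daily visits on Days 4 to 7 (8.1.4) include no ECG.

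**Protocol 8.5.3** uses the same bundle branch block wording, exemption included, to define a cardiac adverse event of special interest (AESI).

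**The concern.** An exemption of this kind normally lets a known, stable finding pass while a new one stops dosing. To do that, its reference point must fall before the period in which the new finding could arise. Here that period runs from inoculation to the Day 8 ECG, and 7.1.1 itself is framed around changes after inoculation. The reference point, however, is the pyronaridine dose, which comes after the decision.

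The participant at issue is one whose Day 8 pre-dose ECG shows right bundle branch block that was absent before inoculation. Protocol 2.2.1 names cardiac events as a risk of the challenge model and relies on ECG recording as a precaution. Under 6.1.2 a listed finding means pyronaridine is not given. An unlisted one can be stopped only by judgement or by meeting another criterion, so listing matters.

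**Working it through.** The plan gives no figure to reproduce; the check is one of logic and counting.

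**Inputs.** One pyronaridine dose, on Day 8 (4.3, 6.1.2). Scheduled ECG time points before it: screening, Day 0 pre-inoculation and Day 8 admission, so 3 (1.3, 8.1.1, 8.1.3, 8.1.5).

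**Item 5 applied to each possible finding at the Day 8 decision**

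| Finding | Predates pyronaridine? | Result as written | Result if tied to inoculation |
|---|---|---|---|
| Right bundle branch block at screening or Day 0 | Yes | Exempt | Exempt |
| Right bundle branch block new between inoculation and the Day 8 pre-dose ECG | Yes | Exempt | Listed stop |
| Right bundle branch block first appearing after the dose | No | Cannot be seen yet | Cannot be seen yet |
| Left bundle branch block, old or new | Not relevant | Listed stop | Listed stop |

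Every right bundle branch block observable at the decision is exempt. An unscheduled ECG on Days 1 to 7 would change nothing, since it too precedes the dose.

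**Count of ECG time points covered by the exemption.** As written: 3 of 3. Tied to inoculation: 2 of 3, with the Day 8 ECG becoming the test. This describes how the wording works and does not measure risk.

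**What entry already screens out.** Inclusion criterion 6 requires QRS of 50 to 120 msec at screening and before inoculation, and a normal tracing unless the abnormality is judged not clinically relevant. Right bundle branch block accepted at entry would therefore have had QRS of 120 msec or less. On Day 8, right bundle branch block with QRS above 120 msec is likely to be new or to have widened since entry, and item 5 exempts it.

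**Whether another item 5 bullet catches it.** The arrhythmia bullet might be argued to, but bundle branch block has its own bullet and its own exemption, so that reading is not secure.

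**The same words in 8.5.3.** AESIs are also assessed after dosing, where the phrase does separate old block from new. It leaves out of the bundle branch block item only right bundle branch block arising between inoculation and dosing. SAP 11.3.1 counts inoculum-emergent events from inoculation, and SAP 11.3.1.2 plans AESI tables on that basis.

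**Cost of one participant not dosed.** 1/6 = 16.7% of a full cohort; 1/18 = 5.6% of the maximum sample; 1/2 = 50% of a Cohort 1 dose group if allocation has already been made. Section 4.1 places randomisation in one sentence on the day of dosing and in another before Day 8; 6.3 places it immediately before dosing.

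**The case against.** The strongest reply is that this is a redundant phrase with adequate cover.

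- **The list is guidance.** So says 7.1.1, and item 6, which expressly covers ECG signals, belongs to the same list. This stands and narrows the gap, although 6.1.2 treats listed criteria as binding while item 6 remains permissive.
- **Other safeguards apply.** Item 1 covers a serious or Grade 3 or higher event. Section 7.2 permits withdrawal "If any clinical AE, laboratory abnormality, or other medical condition or situation occurs" that makes continuing contrary to the participant's interest. Section 8.3.5 requires an Investigator to sign each ECG and to discuss clinically significant findings with the Medical Monitor and Sponsor. SAP 11.6 records the ECG abnormality and its clinical significance. All of this stands.
- **No conduction hazard is documented.** Section 2.2.1 names no conduction block for pyronaridine or the challenge agent; it reports ventricular extrasystoles in two challenge participants. The examples in the opening sentence of 7.1.1 are laboratory changes, and the QTcF limit uses no baseline. This limits the weight of the point but does not make the exemption work.
- **The change is blunt.** It sets no QRS or clinical-significance threshold, so under 6.1.2 even a minor new right bundle branch block would stop dosing. This is a fair cost.
- **Section 8.5.3 may reasonably be tied to the Sponsor's drug.** Accepted; a change there is alignment only.

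**Conclusion.** The point holds as a low-severity correction to safety wording. The item 5 exemption cannot do what it evidently intends, and right bundle branch block new between inoculation and the Day 8 pre-dose ECG is left to discretion. The conclusion rests on a literal reading of the phrase, a single dose, and a deciding ECG that precedes it. The documents give no rate of new right bundle branch block over Days 0 to 8, so no probability is offered.

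Four stronger readings are tempting and are not supported:

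- A reader might infer that any new bundle branch block passes. Left bundle branch block, non-exempt arrhythmia and QTcF above 480 msec remain listed stops.
- A reader might infer that such a participant must be dosed or is unprotected. Items 1 and 6, section 7.2 and mandatory ECG review all allow dosing to be withheld.
- A reader might infer that 8.5.3 is wrong. Its wording works for block arising after dosing. For right bundle branch block new before dosing, what may be lost is the AESI label and, unless the event is serious, the 24-hour report in 8.5.7. A clinically significant block is still recorded as an adverse event.
- A reader might infer harm to the results. The primary PK/PD analysis is unaffected by the present wording.

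**What to change.** In 7.1.1 item 5, replace the exemption with: *except right bundle branch block present before inoculation (screening or Day 0 pre-inoculation ECG)*. The ECGs are already required by inclusion criterion 6, and Protocol 9.4.1 already defines an inoculation baseline, so no new assessment is needed.

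Optionally make the same change in 8.5.3, so that right bundle branch block new before dosing counts as an AESI in the SAP's inoculum-emergent tables. If the sponsor prefers to keep new right bundle branch block a matter of judgement, the protocol should say so openly and drop the qualifier.

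**Cost.** One phrase in one section, or in two with the option. It may count as a substantial amendment needing ethics approval (10.1.2), so it is best bundled with the next one. A participant with new right bundle branch block would receive rescue treatment and contribute no post-dose PK/PD data, with the fractions shown in the working. Section 7.1.1 offers replacement only "If more than two discontinuations pre-IMP administration occur", but 7.2 allows it by agreement between the Sponsor and the Principal Investigator.
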